# 9 Trial procedures

# Recruitment and follow-up:

Following recruitment into the trial, participants will be randomised to one of three arms; intensive intervention, less intensive intervention and control. Those randomised to the intervention groups will be contacted by either the MI counsellor or a member of the research team to arrange a time to meet for the first session. These sessions will be 60 minutes long and will take place at a convenient place for the participants. Individuals in both groups will be telephoned by the MI counsellor at several time points up until 12 months from randomisation. Those allocated to the control group will receive an information pack on lifestyle changes for weight maintenance (the intervention groups will also receive this). Participants will be assessed at six months (from randomisation) during the intervention period by post. We will send two reminders to improve follow-up rates on these questionnaires. The 12 month assessment will be face to face and will be completed by a researcher. A letter will be sent confirming the appointment as well as a text or phone call on the day of the assessment. We will rearrange the face to face sessions twice more if participants fail to attend. In the case of non-responders we will try to complete the key questionnaires over the telephone so that we have a minimum data set.

## Piloting:

Each outcome package (baseline, 6 months and 12) within the trial will be piloted to assess the adequacy of the assessments and presentation. Participant materials (letters, information sheets, posters, leaflets) will also be evaluated. The feasibility and acceptability to participants of materials will be assessed. Piloting will involve lay people acting in an advisory capacity.

#### MI Counsellor Training:

We will develop a training package for the MI counsellors. A manual will be developed by the team for counsellors to try to ensure that the intervention is delivered in a consistent way. The MI counsellors will initially be assessed for their MI skills using the MITI scale and they will be trained in the MI handbook developed by the study team. This details the way we would like the MI delivered within the study. We will also have discussions on the challenges of running MI sessions over the phone and develop guidance in tandem with the MI counsellors on the best way to approach this. The MI counsellors will be given training on issues around obesity as well as diet and physical activity recommendations. We will discuss with them the challenges of weight maintenance and weight loss and how we might best support participants in this process.

# **Process Evaluation:**

We will conduct a process evaluation of the study which aims to:

- assess the delivery of the intervention to ensure that it is provided in accordance with the protocol and delivered consistently
- establish the level of participant adherence to the requirements of the intervention protocol

#### WILMA protocol/version 12.0/21 Aug 2013

- explore participants' views of, and satisfaction with the intervention
- explore MI counsellors experiences of delivering the intervention

The process evaluation will utilise quantitative data from audit of therapist held records and also qualitative data from face-to-face semi-structured interviews with a sample of participants and focus groups with the MI counsellors. We will ask MI counsellors to complete an exit appraisal (included on the MI Case Report Form for the final face-to-face and telephone sessions respectively) for each individual describing what went well and any problems experienced.

#### 1. Assessment of delivery of the intervention

MI counsellors will be asked to audio record as many sessions (face to face and telephone) as possible, with a view to collecting a minimum sample of 6 sessions per counsellor over the course of the study. A random sample of recordings will be assessed using appropriate validated instruments including the MI Treatment Integrity (MITI) coding scale. A stratified sample will include sessions delivered in both intervention arms of the trial and all MI counsellors. Feedback on MITI scores will be given to counsellors. Similarly, recruitment and data collection processes will be audited to ensure standardisation of methods throughout the intervention and data collection periods. Little is currently known about the process of MI and how it relates to outcomes, in particular weight maintenance. Consent will therefore also be sought to use audio-recorded data to examine these relationships, including participant language relating to planning. We propose to qualitatively assess the content of these MI sessions and also to assess how participant/client interactions relate to quantitative outcomes.

# 2. Participant adherence to the protocols

Overall attendance at MI sessions and success of telephone contact will be monitored (number of contact attempts and length of calls will also be recorded). Participant self regulation will be examined by the frequency of self weighing records; counsellor records of recorded goal setting and implementation intentions will also be examined.

The degree of potential contamination across study arms (arising from friends/family members not living together but recruited to different study arms) will be assessed at the end of the 12-month intervention period. We will ask control group participants whether they have been given any information by another study participant, for details of any information received, and whether or not they used the information given. We will ask intervention participants whether they shared study information with other participants, and for details of any information shared.

## 3. Participants' views of the intervention

We propose conducting semi-structured telephone interviews with up to 30 participants in total from the two intervention arms at 6 months (during the intervention); and up to 30 from the intervention arms plus up to 10 control participants at 12 months (following the end of the intervention). We will ask for participants consent to the audio recording of the interviews. An interview specific consent form and information sheet will be sent to participants who express an interest in taking part. The interview will only be arranged once a completed consent form has been returned to the study team. In addition to assessing general views of the way the intervention was delivered, views on efficacy, barriers and facilitators (N.B. we will ask about general views of study participation for controls) we will also examine some potential mediators that are not examined elsewhere.

For example, we will explore: the impact of stressful life events on adherence to the interventions; environmental influences; levels and importance of social support from family and friends; impact on their wider social network; weight maintenance challenges; intrinsic and extrinsic motivations for weight maintenance, health value; body image and its impact; strategies, coping mechanisms and responses to relapses. We will compare the three groups as well as those who maintained weight with those putting weight back on. In addition, we will interview a small sample of participants who drop out of the intervention but who are willing to continue to provide data for research purposes, to establish their views of the trial and/or intervention and reasons for discontinuing. Interviews will continue until all the themes are saturated and participants will be offered a £10 high street voucher for their time in taking part in the interviews.

#### 4. Counsellors views of the intervention:

We will also conduct two focus groups of the MI counsellors to gain their views of the intervention, the perceived challenges or barriers in implementing it and ways they think the intervention and/or training could be improved.

The interviews and focus groups will be audio recorded, transcribed and checked by the researcher.

Participants are likely to want to lose more weight as their BMI will still be high, so although the intervention will target maintenance rather than weight loss, participants may continue to lose weight and we will monitor this.

#### Cost-effectiveness evaluation:

A preliminary cost utility analysis will be undertaken in order to estimate economic parameters and unknowns for future research. (details in section 11.4).

#### 9.1 Data collection/assessment

Baseline and follow-up data will be collected face to face, except for the 6 month assessment which will involve a postal questionnaire. Participants will have their height, weight and waist and hip measured at all time points except the 6 month assessment when just weight will be self assessed. Other data will be collected using paper based methods and researchers will be trained in all aspects of data collection. Data collection at each time point will take 40-50 minutes to complete.

Baseline and outcome data will be collected by the research team and also in Wales by Clinical Studies Officers who are part of the NISCHR Clinical Research Centre and in England the researchers employed by the Comprehensive Local Research Networks. Researchers undertaking the assessment of the outcomes will not have any involvement in the delivery of the intervention. As far as possible they will be blinded to the allocation of the participants, although during interaction with them the group allocation may become apparent. Where this occurs it will be recorded.

#### 9.2 Follow-up

Details of outcomes and follow up time points can be seen in Table 1 and are the same for both experimental and control groups.

#### 9.3 Adverse Events and Serious Adverse Events

**Adverse Event (AE):** Any untoward medical occurrence in a study participant.

**Serious Adverse Event (SAE):** Any untoward and unexpected medical occurrence or effect that:

- Results in death
- Is life-threatening [refers to an event during which the participant was at risk of death at the time of the event; it does not refer to an event which might have caused death had it been more severe in nature]
- Requires hospitalisation, or prolongation of existing hospitalisation
- Results in persistent/significant disability or incapacity
- Is a congenital abnormality or birth defect

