#### Expected AE/SAE

There are no expected AE's/SAE's. Any planned treatments at the start of the study will not be considered as AE's/SAE's.

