#### Related AE/SAE:

The AE/SAE resulted from administration of any of the research procedures (causal to the research process or intervention).

There are no AE's/SAE's expected to be related specifically to the study intervention, although there may be events related to increased physical activity e.g. cardiovascular/musculoskeletal. However, study recommendations for physical activity are in line with the current, widely publicised UK government guidelines. However, the physical activity leaflet and main trial information sheet given to participants state that any increase in physical activity should be gradual and advises participants to contact their GP if they have any concerns or feel unwell as a result of increased physical activity (including experiencing severe breathlessness, chest pain, fainting or dizziness).

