#### Reporting responsibilities:

Where the adverse event meets one of the above categories for an SAE, an SAE form should be completed by the MI counsellor, GP or research team member and faxed to the WILMA Trial Manager within 24 hours of becoming aware of the event. SAEs will also be recorded on the 6-month follow-up questionnaire and follow-up CRFs (i.e. hospitalisations in the preceding 3 months at each time point). In addition, we will ask patients to contact the research team directly by telephone if they are hospitalised at any point during the trial: a member of the research team will then complete an SAE form on the participant's behalf.

[contact]

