#### **Evaluating and reporting:**

The WILMA Trial Manager and the Chief Investigator and the clinical member of the team ([name]) will assess the nature of the SAE for causality and expectedness. Following the initial report, follow up data may be requested by the WILMA Trial Manager. Where the SAE and is both related and unexpected, the WILMA Trial Manager will notify the Chair of the TSC and the main REC within 15 days of receiving notification of the SAE. All SAEs will be recorded and reported annually to the main REC. A standard template will be used to record SAEs.

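### Section 9.3 builds unexpectedness into the SAE definition, which empties the central expectedness assessment; separately, the scheduled SAE question covers only about half of follow-up

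*Protocol*

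**What the plan says.** All of the following is in protocol section 9.3.

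- **AE definition:** "Any untoward medical occurrence in a study participant". It carries no expectedness condition.
- **SAE definition:** "Any untoward and unexpected medical occurrence or effect that" meets one of five listed criteria: death, threat to life, hospitalisation ("Requires hospitalisation, or prolongation of existing hospitalisation"), lasting disability, or congenital abnormality.
- **Expected AE/SAE:** "There are no expected AE's/SAE's". The only exclusion is "Any planned treatments at the start of the study will not be considered as AE's/SAE's".
- **Related AE/SAE:** none is expected to be specific to the intervention, but "there may be events related to increased physical activity", with cardiovascular and musculoskeletal events as the examples.
- **Reporting responsibilities:** an MI counsellor, GP or research team member completes the SAE form when an event falls in one of the SAE categories. The 6-month questionnaire and follow-up CRFs also record SAEs, specified as "hospitalisations in the preceding 3 months at each time point". Participants are further asked to telephone the team about a hospitalisation at any time in the trial, and a team member then completes the form.
- **Evaluating and reporting:** the Trial Manager, the Chief Investigator and the clinical team member "will assess the nature of the SAE for causality and expectedness". Those that are related and unexpected go to the TSC Chair and the main REC within 15 days. All SAEs go to the REC annually.

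**The concern.** Seriousness and expectedness are different questions, normally answered by different people at different times. Here the second is written into the first. Someone who applies the definition as worded has to decide whether an event was unexpected before deciding whether to file a form. The people assigned that judgement see only what has been filed.

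Two things follow. The central assessment becomes circular. And a serious event that a counsellor or GP regards as foreseeable could stop short of central review and, unless another route catches it, be absent from the annual report to the REC. The activity-related events named under Related AE/SAE are the obvious candidates.

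A second, independent weakness is that the only scheduled enquiry about SAEs looks back 3 months at each follow-up, so part of the follow-up period is never actively asked about.

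**Working it through.** The protocol gives no figure to reproduce on this point. The check compares the provisions of section 9.3 and makes one count of months.

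**1. The definition against the central test.** Write S for meeting a seriousness criterion, U for unexpected and R for related.

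- Definition: SAE = S and U.
- 15-day trigger: SAE and R and U = (S and U) and R and U = SAE and R.

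The U in the trigger does no work, because every SAE has already passed it. The central assessment of expectedness can return only one answer. If it is meant to discriminate, U does not belong in the definition.

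**2. Does the statement that nothing is expected settle it?** There are two cases.

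- If reporters apply that statement, U is always true and SAE = S. The qualifier excludes nothing and can be deleted without loss.
- If a reporter instead treats an activity-related event as foreseeable because the protocol names it as possible, then events that are S but not U are not filed by that reporter. Deletion brings them back.

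Deletion is right in both cases.

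**3. Which events rely on the front-line form?**

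| Serious event | Front-line form (definition applies) | Participant telephones (no expectedness test stated) | Scheduled question |
|---|---|---|---|
| Hospitalisation | yes | yes, at any time | yes, 3-month look-back |
| Life-threatening, no admission | yes | not asked for | not asked for |
| Disability, no admission | yes | not asked for | not asked for |
| Congenital abnormality | yes | not asked for | not asked for |

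Both supplementary routes are worded for hospitalisation. The last row can arise in this trial: section 5.2 keeps women who become pregnant after recruitment in the study.

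**4. Coverage of the scheduled question.** Inputs: follow-up at 6 months and at about 12 months with a 3-month window for delay (section 4.2), and a 3-month look-back (section 9.3).

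- Final visit at month 12: months 3–6 and 9–12 are covered. 2 × 3 = 6 of 12 months = 50%. Not asked about: months 0–3 and 6–9.
- Final visit at month 15: months 3–6 and 12–15 are covered. 6 of 15 months = 40%. Not asked about: months 0–3 and 6–12.

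Months 0–3 are when the intensive arm has its fortnightly sessions (section 7). The percentages describe how much of follow-up is actively queried. They do not measure how much reporting is exposed to the word *unexpected*.

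**The case against.** The strongest reply is that the qualifier is inert. The protocol says no event is expected, so a reporter would have to overlook that statement to withhold a form. The remark on physical activity stands under relatedness, calls such events only possible, and does not class them as expected. The trigger for the form can also be read as pointing to the five criteria alone, and no text tells counsellors or GPs to judge expectedness. Counsellors' handbooks cover SAE reporting (section 7), and in the intensive arm months 0–3 are the period of closest contact. This largely stands. It makes misuse of the definition unlikely, but it does not remove the contradiction with the central assessment, and it offers no reason to keep the word.

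A reader might infer that activity-related hospitalisations have no way of being reported. The documents do not support that: the request to telephone covers any hospitalisation throughout the trial and leads to an SAE form with no expectedness test. For the same reason, a reader should not infer that the months outside the look-back rest only on reports filtered by the definition. The telephone route does depend on the participant remembering to call.

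On the look-back, section 11.4 justifies 3 months by the validity of recall. That justification concerns health service resource use and stands for that purpose. An admission is asked about here for a different reason. It is also fair that recruitment has closed (section 10.2), so a reworded question would apply to only part of follow-up.

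**Conclusion.** The contradiction is real and follows from the wording alone: expectedness cannot be both a condition of being an SAE and a property judged centrally afterwards. Its practical reach is narrow. The residual risk falls mainly on serious events without admission, and on admissions that the participant does not telephone about, in either case where a reporter reads the activity-related examples as making an event foreseeable. How many events that might be cannot be derived from the protocol. Nor does the protocol support a claim that the harms most plausibly caused by the intervention are the ones most likely to be lost.

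The limited look-back is a separate gap: 6 of 12 months actively queried, or 6 of 15 at the latest final visit. This assumes the two follow-ups of section 4.2, completed on time apart from the stated window.

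The point should be corrected because it concerns safety reporting and the remedy is nearly free. It does not undermine the trial's main feasibility outcomes.

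**What to change.** 1. In the SAE definition in section 9.3, delete the two words that add unexpectedness, so that meeting a seriousness criterion alone makes an untoward event an SAE. Leave expectedness to the central assessment under Evaluating and reporting, where it then has a real function in the 15-day rule.
2. For SAE capture, have the 6-month questionnaire and the 12-month CRF ask about hospitalisations since the previous assessment (since randomisation at 6 months). Keep the 3-month recall for resource use in section 11.4 as a separate item.

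The cost is two words, one reworded form question and a few more SAE forms. Recall becomes longer, about 6 months and up to 9 if the final visit is at month 15 (15 − 6 = 9), so some admissions will be reported less exactly. Because the form would change part-way through follow-up, the version each participant completed should be recorded, so that any difference in capture can be seen when SAEs are summarised.

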#### Expected AE/SAE

There are no expected AE's/SAE's. Any planned treatments at the start of the study will not be considered as AE's/SAE's.

#### Related AE/SAE:

The AE/SAE resulted from administration of any of the research procedures (causal to the research process or intervention).

There are no AE's/SAE's expected to be related specifically to the study intervention, although there may be events related to increased physical activity e.g. cardiovascular/musculoskeletal. However, study recommendations for physical activity are in line with the current, widely publicised UK government guidelines. However, the physical activity leaflet and main trial information sheet given to participants state that any increase in physical activity should be gradual and advises participants to contact their GP if they have any concerns or feel unwell as a result of increased physical activity (including experiencing severe breathlessness, chest pain, fainting or dizziness).

#### Reporting responsibilities:

Where the adverse event meets one of the above categories for an SAE, an SAE form should be completed by the MI counsellor, GP or research team member and faxed to the WILMA Trial Manager within 24 hours of becoming aware of the event. SAEs will also be recorded on the 6-month follow-up questionnaire and follow-up CRFs (i.e. hospitalisations in the preceding 3 months at each time point). In addition, we will ask patients to contact the research team directly by telephone if they are hospitalised at any point during the trial: a member of the research team will then complete an SAE form on the participant's behalf.

[contact]

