# 4.2 Frequency & duration of follow-up

Following baseline assessments participants will be followed up at 6 months during the intervention by postal questionnaire. Participants will be followed up by a researcher at the end of the intervention (approximately 12 months after randomisation with a 3 month window to allow for any delay)..

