#### MI session content

MI counsellors will be given a handbook to guide the sessions, comprising the following information: a summary of the client group and their challenges, MI within the context of weight maintenance and intervention 'hot topics': self-monitoring; goal-setting and implementation intentions; habits; emotional eating and coping with relapse; diet; exercise; barriers to maintenance; social support and self-efficacy. Information on study-specific procedures (reporting Serious Adverse Events, lone-working, actual/risk of self-harm to participants and administrative processes) is also included. MI counsellors will keep a written record of each face-to-face and telephone session (including goal setting and implementations intentions) using the appropriate Case Report Form (CRF).

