#### 11.4 Economic evaluation

There are limitations to undertaking a cost utility analysis within a feasibility study. Although we will not be able to establish definitive cost utility results, we will apply a cost utility framework to estimate parameters and unknowns for future research. Direct costs will include all resources used in the delivery of the interventions (staff time, staff travel, materials, venue, etc.). These will be recorded prospectively in relevant units and valued using standard methods. All resources used in training professionals in motivational interviewing skills will similarly be prospectively recorded and valued. As training is a one off investment which produces a flow of benefits over time, training costs will be amortised similarly to equipment expenditures.

Indirect costs will include differential use of NHS resources. Health service resource use in primary care, secondary care and the community will be collected for participants in all 3 arms of the trial at baseline, 6 months (during the intervention) and at 12 months. Questions will relate to all health service contacts and prescription medicines dispensed in the previous 3 months. Patient recall has been shown to be a valid method for collecting health service resource use data over this period. Health service resource use will be valued using standard sources. All costs relating to weight loss/maintenance activities such as use of gyms will be recorded. It is important to monitor these costs as the intervention may be substituting for some activities, for example weight loss group sessions by participants in the control group. Mean differential costs will be estimated. As cost data are often skewed, tests for normality will be applied. If distributions are shown to be nonnormal, non-parametric bootstrapping methods will be used to test for mean cost differences between groups.

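### The only prompted SAE question covers 6 of the 12 months of follow-up, and in the unasked months one of the reporting routes depends on counsellor contact that differs by arm

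*Protocol*

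**What the plan says.** Section 9.3 (Reporting responsibilities) sets up three ways for an SAE to reach the trial team.

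- **On awareness.** When an event qualifies, "an SAE form should be completed by the MI counsellor, GP or research team member", to be sent within 24 hours of that person learning of it.
- **Prompted at assessments.** "SAEs will also be recorded on the 6-month follow-up questionnaire and follow-up CRFs (i.e. hospitalisations in the preceding 3 months at each time point".
- **Participant telephones.** "we will ask patients to contact the research team directly by telephone if they are hospitalised at any point during the trial"; the team then completes the form.

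The 6-month assessment is a postal questionnaire. The final one is a researcher visit, "approximately 12 months after randomisation with a 3 month window to allow for any delay" (section 4.2). Section 7 gives the counselling schedules, and of the counsellors' handbook it says: "Information on study-specific procedures (reporting Serious Adverse Events, lone-working, actual/risk of self-harm to participants and administrative processes) is also included".

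Section 11.4 uses the same look-back for health service use: "Questions will relate to all health service contacts and prescription medicines dispensed in the previous 3 months".

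**The concern.** A 3-month look-back at assessments 6 months apart cannot cover the time between them. The first unasked stretch is the first three months after randomisation. In the intensive arm that is when all the face-to-face sessions take place, and section 2.2 says the main part of the intervention falls in the first five to seven months. Section 9.3 expects no related events, but it allows that increased physical activity might lead to cardiovascular or musculoskeletal ones.

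Two things are at stake. The first is completeness: section 9.3 requires all SAEs to be recorded and reported annually to the ethics committee, and an admission in month 2 or month 8 is recorded only if someone volunteers it. The second is comparability: where no common question is asked, the chance of an event coming to light depends partly on how often a participant speaks to a counsellor, and that is what the arms were designed to vary. The analysis plan is not at hand, but no analysis plan could recover admissions that nobody asked about.

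**Working it through.** The protocol states no coverage figure to reproduce, so coverage is computed directly.

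**Inputs**
- Look-back: 3 months (section 9.3).
- First follow-up assessment: month 6. Final assessment: month T, with T from 12 to 15 (section 4.2).
- The SAE item sits on the 6-month questionnaire and the follow-up forms, so baseline adds no time after randomisation.

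**Coverage**

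Asked: months 3 to 6 and months T − 3 to T, together 3 + 3 = 6 months.
Unasked: months 0 to 3 and months 6 to T − 3, together T − 6 months.
Unasked share = (T − 6)/T.

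| Final visit T | Asked | Unasked | Unasked share | Unasked periods |
|---|---|---|---|---|
| 12 | 6 | 6 | 6/12 = 50% | 0-3 and 6-9 |
| 13 | 6 | 7 | 7/13 = 54% | 0-3 and 6-10 |
| 14 | 6 | 8 | 8/14 = 57% | 0-3 and 6-11 |
| 15 | 6 | 9 | 9/15 = 60% | 0-3 and 6-12 |

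**Routes open in the unasked months**
- Participant telephone call: all arms, unprompted.
- GP report: all arms, unprompted.
- Counsellor report: the two intervention arms only, whenever a counsellor becomes aware of an event.

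**Scheduled counsellor contacts (section 7)**

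| Arm | Face to face | Telephone | Total | Within months 0-3 and 6-9 |
|---|---|---|---|---|
| Intensive | 6, fortnightly over three months | 9, monthly for the last nine months | 6 + 9 = 15 | 6 + 3 = about 9 |
| Less intensive | 2, two weeks apart | 2, at months 6 and 12 | 2 + 2 = 4 | 2, if the sessions fall soon after randomisation |
| Control | 0 | 0 | 0 | 0 |

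The less intensive arm's month-6 call falls on the edge of the second gap and is not counted inside it.

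**With the item reworded**

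If the 6-month form asks about months 0 to 6 and the final form about months 6 to T, the asked time is 6 + (T − 6) = T and the unasked share is 0 for anyone who completes both.

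**The case against.** The strongest reply is that the unasked months are not without a reporting system. Every participant is asked to telephone after any hospitalisation during the trial. GPs are named reporters and are told that their patient is taking part (section 6.2). Both routes run throughout and are the same in all arms. This stands: what is missing is a prompted question, and only one of the remaining routes differs by arm. It does not close the gap, because both common routes rely on someone remembering to volunteer the event.

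A reader might infer that the intensive arm will show more SAEs simply because counsellors ask. The protocol does not support that. It gives counsellors a procedure for reporting SAEs, but the listed session topics include no enquiry about admissions. SAEs are not among the outcomes in section 4.3 or Table 1, and section 11 plans no comparison of SAE counts by arm. More contact may bring more events to light; that it will, and by how much, cannot be shown.

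A reader might also infer that the cost-utility ratio sets half a year of NHS costs against a full year of QALYs. That is not supported either. The 3-month recall for resource use is deliberate and is justified in sections 8.1 and 11.4. The protocol nowhere says that the observed costs enter the ratio unscaled, and the handling of the unobserved months may be in an analysis plan not shown. Section 11.4 also disclaims definitive cost-utility results.

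Finally, this is a behavioural feasibility study with no related SAEs expected and recruitment already closed. That lowers the urgency, but the final visit can still ask the question.

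**Conclusion.** The point holds for SAE ascertainment. The only prompted item leaves 6 of 12 months unasked, and up to 9 of 15 for a visit at the end of the window. The gap includes the first three months of the intervention. In those months the counsellor route offers 15, 4 and 0 scheduled contacts over the whole schedule, of which about 9, 2 and 0 fall inside the gaps for a 12-month final visit. SAEs may be missed, and any description of them by arm may be affected by unequal detection.

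The coverage figures assume that the 6-month form is completed at month 6. The contact counts assume the schedule is delivered as written and that the two less intensive sessions come early. The number of events missed and the size and direction of any difference between arms cannot be computed, because the protocol gives no admission rate and no rate of unprompted reporting. The conclusion does not extend to the economic evaluation.

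**What to change.** Reword the hospitalisation/SAE item on two forms:

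- on the 6-month questionnaire, ask about the whole time since randomisation;
- on the final case report form, ask about the whole time since the last assessment;
- for anyone already past the 6-month form, ask at the final visit about the whole period since randomisation.

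Base any summary of SAEs by arm on this common prompted item, and keep the telephone, GP and counsellor routes for prompt reporting. Leave the 3-month recall for other health service use as it is.

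The cost is an amendment and one changed item on two forms, with no extra visit. Recall lengthens from 3 to about 6 months, or to the full 12 to 15 months for those asked only at the end; an admission is a salient event, so the loss should be small. Two limits remain. Retrospective questioning improves the completeness of the record but does not serve the 24-hour reporting rule. Participants lost before the final visit, whom section 6.5 puts at around 30%, still have only the unprompted routes after their last completed form.
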